4.8. Efficacy Endpoints

4.8.1. General Analysis Methods for Efficacy Endpoints

ALSFRS-R, SVC, HHD, [REDACTED], and time to death or permanent ventilation will not be summarized or analyzed based on baseline of 233AS102, but these data will be combined with data from 233AS101 and summarized and analyzed based on the ISE SAP.

4.9. Safety Endpoints

The safety population will be used for the analyses of the safety data. Safety data will be summarized using frequency counts and percentages and descriptive statistics by study group.

A summary of missing safety data by visit and overall (i.e. C-SSRS, laboratory data broken down by panel, vital signs) will be presented. The summary will also be broken down by whether the visit was missed due to COVID-19 or other reason. Missing summary will not be performed for MMSE, ECG and neurological examination due to only limited data collected based on protocol amendment V6.0; MMSE was removed and all dosing visits were removed for ECG and neurological.

4.9.1. Adverse Events

All AEs will be classified using MedDRA version 27.0 or later. All AEs will be listed but only treatment emergent AEs will be summarized, where treatment emergence will be relative to the first dose of study drug. A treatment emergent AE/SAE is defined as any AE/SAE with an onset date and time that is on or after the first dose of study drug or any pre-existing condition that has worsened in severity after the first dose of study drug. In case of missing dates,

- Any AE/SAE with both a missing onset date and resolution date, or any AE/SAE with a missing onset date and a resolution date which is after the first dose of study drug, will be considered treatment emergent.
- If the onset date is available but onset time is missing and the AE onset date is the same as the first dose date the AE will be considered treatment emergent.
- For AEs with a partial start date, the year/month of the event date will be compared to that of the first dose date to determine whether the event is treatment emergent.

The incidence of treatment emergent AEs will be summarized by study group as follows:

- by primary system organ class (SOC) and MedDRA preferred term sorted by decreasing frequency
- by SOC and MedDRA preferred term sorted by alphabetical order
- by MedDRA preferred term
- by SOC

- The most common treatment emergent AEs i.e. occurring in $\geq 5\%$ subjects in any study group will be presented by MedDRA preferred term.
- For Part C subjects only, the most common treatment emergent AEs i.e. occurring in 2 or more subjects in subjects previously on tofersen in 233AS101 compared to subjects who were on placebo will be presented by MedDRA preferred term.
- By maximum CTCAE grade, primary SOC and MedDRA preferred term
- By maximum CTCAE grade and MedDRA preferred term
- AEs with a CTCAE grade ≥ 3 by primary SOC and MedDRA preferred term
- Related AEs by primary SOC and MedDRA preferred term
- SAEs by primary SOC and MedDRA preferred term
- SAEs by MedDRA preferred term
- Related SAEs by primary SOC and MedDRA preferred term
- AEs related to lumbar puncture (as assessed by the investigator) by primary SOC and MedDRA preferred term
- AEs that occurred within 24 hours of dosing by primary SOC and MedDRA preferred term (in case of partial AE start date, if the month and year are available and day is missing, the AE will be included for any dose that occurs in the same month and year as the AE)
- AEs which led to discontinuation of study drug by primary SOC and MedDRA preferred term
- AEs which led to withdrawal from study by primary SOC and MedDRA preferred term
- AEs which led to drug interrupted by primary SOC and MedDRA preferred term
- AEs which led to hospitalization by primary SOC and MedDRA preferred term (showing number and percentage of subjects with at least one occurrence in that SOC or preferred term, as well as total number of events). Further summaries of hospitalization data are also included later in this section.
- AEs that led to death
- AEs of note (serious neurologic events, falls, CSF laboratory abnormalities) for which preferred terms will be based on a medical review before final analysis and unblinding. This summary will include number and percentage of subjects with at least one event and total number of events. The follow-up adjusted incidence rates based on number of subjects as well as number of events will also be presented in the same table. If any of these are defined based on more than one preferred term, the preferred terms will also be broken down under the overall category.

The sorting order for AE incidence tables, unless otherwise specified, will be by decreasing frequency order of “Total tofersen all doses” column. For the AE summary by primary system organ class and preferred term, subjects will be counted only once within each primary SOC/MedDRA preferred term. For the summary of AEs by maximum CTCAE grade, primary system organ class and preferred term, subjects will be counted only once within each primary SOC/MedDRA preferred term and will only be counted under the maximum CTCAE grade. For the summary of related AEs, if the relationship is missing then this will be summarized as unknown.

For AEs that occurred within 24 hours of dosing, if time of AE is missing and the event occurs on the same day as the day for dosing or the day following dosing, the AE will be counted as occurring within 24 hours of dosing.

An overall summary of AEs will also be presented. A separate table will also be presented to show an overall summary of COVID-19 pandemic related AEs.

Listings of the following events will be produced.

- AEs which led to discontinuation of study drug
- AEs which led to withdrawal from study
- AEs which led to drug interrupted
- AEs related to lumbar puncture
- AEs which led to hospitalization
- SAEs
- AEs

A listing of deaths will be provided if applicable.

An additional table for hospitalizations will present the number and percentage of subjects in each treatment group with at least one hospitalization, the number of hospitalizations per subject, total number of hospitalization and a descriptive summary for the total cumulative duration of hospitalizations per subject.

Pre-treatment SAEs i.e. those that occurred between screening and first dose are not considered treatment emergent and so will be summarized separately if there is a sufficient number. Pre-treatment AEs should not be collected unless classed as serious. All SAEs will be listed, with an indicator for pre-treatment SAEs. Only treatment emergent AEs will be summarized, unless otherwise specified.

A separate summary will be presented for each confirmed COVID-19 AE and suspected COVID-19 AE. These will be identified as AEs that are recorded with an entry of '(Confirmed)' and '(Suspected)'. As per the guidance, confirmed cases are those confirmed via a diagnostic test and suspected cases are those diagnosed based on typical symptoms, travel/contact history. A listing will also be provided.

Incidence rate tables

Incidence and incidence rate will be provided in incidence rate tables and will be summarized by primary SOC and MedDRA preferred term by study group. Two different kinds of incidence rate tables will be provided. Definitions are provided below:

- 1) Follow-up adjusted incidence rate – defined as the number of subjects who experienced an event divided by the total of entire follow-up time among the subjects in the analysis population. The entire follow-up time for subject is defined as the time from the first dose until the last day (the earliest date of last study day and interim cutoff date) on study. Each subject will be counted only once within each category. A similar table will also be based on total number of events divided by the total of entire follow-up time among the subjects in the

analysis population. This may count a subject more than once within each category of they experienced an event more than once.

- 2) Exposure-adjusted incidence rate (EAIR) – defined as the number of subjects who experience an event divided by the total exposure adjusted follow-up time among the subjects in the analysis population. The exposure adjusted follow-up time is defined as the time from the first dose until the initial occurrence of the event for those who experienced an event, or from the first dose until the end of follow-up (the last day (the earliest date of last study day and interim cutoff date) on study) for those who did not. Each subject will be counted only once within each category. If the initial occurrence of the event has a partial start date, the following rules will be applied. If only month and year of the AE are available, and the month and year are same as that of the first dose then it will be assumed that the event started on date of first dose. Otherwise it will be assumed that the event started on the first of the month. If only year is available, and the year is same as that of the first dose then it will be assumed that the event started on the date of first dose. Otherwise it will be assumed that it started on the 1st January.

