7.2. Overall Study Duration and Follow-Up

The overall duration of study participation for a single participant will be up to 368 weeks, which includes an approximately 4-week screening period, up to a 360-week treatment period, and a 4-week follow-up period.

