16.2. Clinical Function

16.2.1. Methods of Analysis

As this is an open-label, long-term extension study, analyses will be exploratory and descriptive in nature.

Data will be summarized using descriptive statistics for continuous variables and using frequency and percentage for discrete variables. For participants who have completed Parts A or B of Study 233AS101, the time trajectory of each clinical function may be summarized at selected timepoints and presented in plots. For participants who have completed Part C of Study 233AS101, the time trajectory will be summarized by the prespecified subgroup (enriched population versus other eligible participants) and the prior treatment received during Study

CONFIDENTIAL

The information contained herein may not be used, disclosed, or published without the written consent of Biogen MA Inc.

233AS101 from the baseline of Study 233AS101 (including data from Studies 233AS101 and 233AS102), from the baseline of Study 233AS102 (including data from Study 233AS102 only), and from the start of BIIB067 100 mg dosing.

Efficacy will be measured based on changes in ALSFRS-R, percent predicted SVC, HHD Megascore and individual muscle strength, [REDACTED]. Changes from baseline (using definitions outlined above) will be summarized over time for each of these endpoints.

Analysis of covariance using multiple imputation will be performed at selected timepoints, based on level of data available at interim and final analysis.

Time to death or permanent ventilation (i.e., ≥ 22 hours of mechanical ventilation [invasive or noninvasive] per day for ≥ 21 consecutive days) and time to death will be summarized using Kaplan-Meier curves based on the starting time using the following:

1. Entry into Study 233AS101
2. Entry into Study 233AS102
3. The start of BIIB067 100 mg dosing
4. Time of symptom onset

The relationship between PK or PD endpoints and the clinical function endpoints will also be explored.

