21. SIGNED AGREEMENT OF THE STUDY PROTOCOL

I have read the foregoing protocol, "An Extension Study to Assess the Long-Term Safety, Tolerability, Pharmacokinetics, and Effect on Disease Progression of BIIB067 Administered to Previously Treated Adults with Amyotrophic Lateral Sclerosis Caused by Superoxide Dismutase 1 Mutation," and agree to conduct the study according to the protocol and the applicable ICH guidelines and GCP regulations, and to inform all who assist me in the conduct of this study of their responsibilities and obligations.

Investigator's Signature

Date

Investigator's Name (Print)

Study Site (Print)

CONFIDENTIAL

The information contained herein may not be used, disclosed, or published without the written consent of
Biogen MA Inc.

Biogen MA Inc.
[name]
Cambridge, MA 02142
United States

Biogen Idec Research Limited
[name]
[name]
Maidenhead, Berkshire
SL6 4AY
United Kingdom

AMENDMENT SUMMARY

Biogen Protocol 233AS102

An Extension Study to Assess the Long-Term Safety, Tolerability, Pharmacokinetics, and Effect
on Disease Progression of BIIB067 Administered to Previously Treated Adults with
Amyotrophic Lateral Sclerosis Caused by Superoxide Dismutase 1 Mutation

Version 6

Date: 04 August 2021

EUDRA CT Number: 2016-003225-41

Version 6 of the protocol has been prepared for this amendment, which supersedes Version 5.

CONFIDENTIAL

The information contained herein may not be used, disclosed, or published without the written consent of
Biogen MA Inc.

PRIMARY REASON FOR AMENDMENT

The primary reason for this amendment to Protocol 233AS102 is to extend the maintenance dosing portion of the treatment period of the study by up to 124 weeks while minimizing the burden on participants. Maintenance dosing will continue for all participants until the LPI has had the opportunity to reach Week 152 of the maintenance dosing period, which for the first participant in is Week 360. The maintenance dosing period will be followed by a Final Visit at 4 weeks after the last dose. This extends the study until the LPI reaches Week 156. Changes to the study visits include the following:

- The Follow-Up Visits before the Final/Early Termination visit will be eliminated.
- The Final or Early Termination Visit will now be held 4 weeks after the last dose.
- SVC and HHD will be completed every 12 weeks instead of every 4 weeks during the maintenance dosing period.

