Change: The frequency of the [REDACTED] and Mini-Mental State Examination (MMSE) assessments were reduced. Examination of the cranial nerve was removed as a component of the limited neurological examination. Pregnancy testing was changed to allow testing to be done on either urine or serum.

CONFIDENTIAL

The information contained herein may not be used, disclosed, or published without the written consent of Biogen MA Inc.

Now reads:

Assessments	Screening Visit ¹	Baseline/1 st Loading Dose Visit			2 nd Loading Dose Visit			3 rd Loading Dose Visit			Maintenance Dose Visit			Follow-Up Visits	Final or Early Termination Visit
	Week -4 to Day -1	Day 1			Day 15 (± 3 days) (Week 2)			Day 29 (± 3 days) (Week 4)			Weeks 8, 12, 16, and every 4 weeks thereafter up to Week 236 (± 3 days)			Weeks 240 and 244 (± 7 days) (4 and 8 weeks after last dose)	Week 248 (± 7 days) or 12 weeks after last dose [Early Termination Visit]
		Pre dose	LP	Post dose	Pre dose	LP	Post dose	Pre dose	LP	Post dose	Pre dose	LP	Post dose		
Limited Neurological Examination (including MMSE) ¹²¹⁴	X	X ¹⁰		X	X ¹⁰		X	X ¹⁰		X	X ¹⁰		X	X	X
MMSE	X	X		X							X ¹¹		X ¹¹		X
Urine Pregnancy Test ¹³¹⁵	X	X ¹⁰			X ¹⁰			X ¹⁰			X ¹⁰				X

⁵ May be performed at any time on the day prior to study treatment administration, or predose on the day of study treatment administration, or over 2 days at the Follow-up Visits (Weeks 240 and 244) and Final or Early Termination Visit.

¹⁰To be collected/Performed predose.

¹¹To be performed at Week 12, 24, 36, and 48 Visits (i.e., every 12 weeks); Week 72, 96, 120, 144, 168, 192, and 216 Visits (i.e., every 24 weeks); and Week 228 Visit.

¹²¹⁴ The components of the limited neurological examination are cranial nerves, coordination/cerebellar function, reflexes, and motor system, and MMSE.

¹³¹⁵ To be performed only in women of childbearing potential; results must be negative to continue participation in study. On dosing days, samples must be analyzed before study treatment administration. To be performed via urine or serum testing.

CONFIDENTIAL

The information contained herein may not be used, disclosed, or published without the written consent of Biogen MA Inc.

Rationale:

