QTc	interval between the start of the QRS complex and the end of the T wave, corrected for heart rate
QTcF	QTc interval using Fridericia's formula
RBC	red blood cell (count)
RNA	ribonucleic acid
RR	inter-beat
SAE	serious adverse event
SAP	statistical analysis plan
SAS	statistical analysis system
SD	standard deviation
SDTM	standard data tabulation model
SE	standard error
[REDACTED]	[REDACTED]
SOC	system organ class
SOD	superoxide dismutase 1
SVC	slow vital capacity
ULN	upper limit of normal
WBC	white blood cell (count)
WHO	World Health Organization
[REDACTED]	[REDACTED]
[REDACTED]	[REDACTED]

1. Introduction

Study 233AS102 is an extension study of 233AS101 to assess the long-term safety, tolerability, pharmacokinetics, pharmacodynamics, and efficacy of BIIB067 administered to previously treated adults with ALS caused by SOD1 mutation, who have completed Parts A, B, or C of Study 233AS101.

Study 233AS101 is a randomized, double-blind, placebo-controlled, 3-part study to examine the efficacy, safety, tolerability, pharmacokinetics (PK), and pharmacodynamics (PD) of BIIB067, administered by intrathecal bolus injection in subjects with ALS and a confirmed SOD1 mutation.

This statistical analysis plan (SAP) is prepared to describe the final analysis for the closeout clinical study report for 233AS102; separate SAPs exist for 233AS101 Parts A and B, 233AS101 Part C, and integrated analyses across the studies. Prior versions of the SAP for 233AS102 (Versions 1.0 to 3.0) were generated for the purpose of interim analyses based on interim data cuts for the study.

BIIB067 will be referred to as tofersen throughout the rest of the statistical analysis plan.

There are limitations for subjects who enrolled from 233AS101 Parts A and B which impact the interpretability of these subjects in 233AS102:

- Subjects who completed Parts A or B of 233AS101 had a significant washout period ranging from 16 weeks to over 2 years from their last dose of study treatment in 233AS101 to their first dose in 233AS102.
- Dosing paradigms varied substantially across subjects as dose levels in 233AS102 were increased over time as additional doses were deemed to have an acceptable safety profile in 233AS101.
- Many subjects had meaningful disease progression during the washout and exposure to lower doses resulting in a large proportion of discontinuations across studies

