3.1. Dates and Points of Reference

- Study Day 1: the date of the first dose of study treatment in 233AS102
- Study Day
 - For a date on or after Study Day 1
$$\text{Study Day} = (\text{Date of Interest}) - (\text{Study Day 1}) + 1$$
 - For a date before Study Day 1
$$\text{Study Day} = (\text{Date of Interest}) - (\text{Study Day 1})$$
- Unless stated otherwise, baseline data are defined as the data collected prior to the time and/or on the date of first dose, which is usually the same day as the Day1/Baseline visit in 233AS102. If there is more than one value on/before the date of the first dose, the non-missing value closest to and prior to the first dose will be used as the baseline value
- *Visit window for analysis*

If, due to the COVID-19 pandemic, subjects could not attend clinic visits during protocol defined visit windows, they were given some allowance to have a delayed visit. There may also have been subjects who attended visits outside of the protocol defined windows for other reasons. Regardless of whether the delayed visit was due to the COVID-19 pandemic or not, these are recorded under scheduled visits and are also considered to be protocol deviations. Visit windows will not be applied to scheduled visits for analysis purposes. If a subject had a phone visit followed by a delayed clinic visit, the clinic visit is still recorded as the scheduled visit. The scheduled visit will always take precedence over unscheduled visits.

For subjects who are early terminated (ET), EOS visit is defined as the scheduled follow-up visit 4 weeks after last dose. Data from early withdrawal visits and post

baseline unscheduled assessments will be assigned to an appropriate scheduled post baseline visit using a windowing scheme for assessments that are tabulated or summarized by visit. Scheduled visits will not be windowed.
The visit windowing for endpoints is given in the table below:

Table 3 Visit Windows for Safety Endpoints and CSF PK Endpoints

Visit	Safety Endpoints and CSF PK Concentration*		
	Lower Bound (Day)	Upper Bound (Day)	Target Day
Week 2 (Day 15)	8	21	15
Week 4 (Day 29)	22	42	29
Week 8	43	70	57
Week 12	71	98	85
Week 16	99	126	113
Week 20	127	154	141
Week 24	155	182	169
Week 28	183	210	197
...
Week 352	2451	2478	2465
Week 356	2479	2506	2493
Week 360	2507	2534	2521
Week 364	2535	2562	2549

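### Treatment emergence has no end point relative to the last dose, so the AE, SAE and fatal-AE percentages mix 12-week (before Protocol Version 6) and 4-week (Version 6) post-dose collection windows

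*SAP*

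**What the plan says.** SAP 4.9.1 defines a treatment-emergent AE or SAE as "any AE/SAE with an onset date and time that is on or after the first dose of study drug", or a pre-existing condition that worsens after that dose. No rule refers to the last dose. The incidence of all such AEs, of SAEs and of AEs leading to death is then tabulated by study group. SAP Table 6 sets the two Part C columns, the pooled Part A+B column and the total side by side. The same section adds follow-up-adjusted incidence rates and exposure-adjusted incidence rates (EAIRs).

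Protocol 15.3.1 ends AE recording at the last study visit. Protocol 15.3.2 ends SAE recording at the final study visit, after which only SAEs judged related are reported. The length of the post-dose window therefore follows the visit schedule.

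The Version 6 amendment summary states: "The Final or Early Termination Visit will now be held 4 weeks after the last dose". It lists Sections 15.3.1 and 15.3.2 among the sections affected. The schedule in the Version 5 amendment summary shows the last visit at "Week 248 (± 7 days) or 12 weeks after last dose [Early Termination Visit", with follow-up visits at 4 and 8 weeks. The amendment history is used here only as evidence of how the pooled data were collected. That it differs from the current text is not an error.

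SAP 2.3 and Table 2 list what the amendments did to each endpoint. They do not mention the shortened follow-up, and neither does SAP 5.

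**The concern.** The primary endpoint is the incidence of AEs and SAEs, and the final SAP pools data collected under several protocol versions. A subject who left under Version 5 or earlier was due to be asked about events for 12 weeks after the last dose. A subject who leaves or completes under Version 6 is asked for 4 weeks, or longer if dosing stops but the subject stays in the study.

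Protocol 5.1 describes ALS as declining to death from respiratory failure, so unrelated serious events soon after the last dose are to be expected. Under Version 6, an unrelated SAE that starts after the 4-week visit need not be reported. Under the earlier schedule the same event would have been recorded.

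Protocol version may also be related to study group. SAP 2.3 says that Part C subjects began to enter at Version 4, after Parts A and B. The SAP Introduction says that Part A/B subjects progressed, "resulting in a large proportion of discontinuations across studies". A reader comparing columns cannot tell how much of a difference comes from the length of the post-dose window.

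**Working it through.** **Schedule check**
- Version 6 total participation (Protocol 7.2): "which includes an approximately 4-week screening period, up to a 360-week treatment period, and a 4-week follow-up period". 4 + 360 + 4 = 368 weeks, as stated.
- Version 4 total (amendment summary): 4 + 236 + 12 = 252 weeks, as stated there.
- Post-dose window under Version 5: Week 248 − Week 236 = 12 weeks. Under Version 3: Day 729 − Day 645 = 84 days = 12 weeks.
- Post-dose window in SAP Table 3: Week 364 − Week 360 = 4 weeks.

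**Who can have a 12-week window.** From Version 4 (11 January 2019) to Version 6 (4 August 2021) is 134 weeks, short of Week 236. A Part C subject with a 12-week window is therefore, in all likelihood, one who left early. Two assumptions are made: Version 6 took effect on its document date, and the alternative Version 5 stop, at the last subject's Week 92, had not been reached. Part C leavers before Version 6 had 12 weeks too, so the split is by date of leaving and not by study group.

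**Ratio of windows.** Per subject it is 12/4 = 3.0. For a group in which a share f ended under Version 5 or earlier, the mean scheduled window is 12f + 4(1 − f). The documents do not give f, so the shares below are assumptions.

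| f, group 1 | f, group 2 | Mean windows (weeks) | Ratio |
|---|---|---|---|
| 0.9 | 0.1 | 11.2 and 4.8 | 2.33 |
| 0.8 | 0.2 | 10.4 and 5.6 | 1.86 |
| 0.7 | 0.3 | 9.6 and 6.4 | 1.50 |
| 0.5 | 0.5 | 8.0 and 8.0 | 1.00 |

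**Total observation.** With the last dose at week T, the ratio of whole collection windows is (T + 12)/(T + 4). It is 36/28 = 1.29 at Week 24, 64/56 = 1.14 at Week 52 and 164/156 = 1.05 at Week 152. At Week 24 the off-treatment share of the window is 12/36 = 33% against 4/28 = 14%.

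**Effect on crude incidence.** Assume a constant rate r per person-year and a subject free of the event at the last dose. The probability that the first event falls in weeks 4 to 12 is exp(−4r/52.18) − exp(−12r/52.18):
- r = 0.1: 1.5 points
- r = 0.25: 3.7 points
- r = 0.5: 7.1 points
- r = 1.0: 13.2 points

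A group percentage moves by less, because only a share f is affected and a subject already counted for a term is not counted again. With f = 0.8 against 0.2, the difference between groups is at most 0.6 times these figures, or 0.9 to 7.9 points.

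**Direction.** At r = 0.25, crude incidence 1 − exp(−r × weeks/52.18) is 15.8% for a Week 24 leaver followed for 36 weeks, 12.6% for one followed for 28 weeks, and 52.6% for a Week 152 completer followed for 156 weeks. Length of treatment matters far more than the extra 8 weeks.

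**Time-adjusted rates.** If the event rate after stopping is k times the on-treatment rate, the observed event rate relative to the on-treatment rate is (T + kW)/(T + W) for a post-dose window of W weeks. With k = 1 it is 1 for any W, so the rate is unaffected. With k = 2 (assumption) and T = 24 it is 48/36 = 1.33 for W = 12 and 32/28 = 1.14 for W = 4, a ratio of 1.17. At T = 52 it is 76/64 = 1.19 against 60/56 = 1.07, a ratio of 1.11.

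**The case against.** **The SAP already adjusts for unequal observation.** The follow-up-adjusted rates and EAIRs of SAP 4.9.1 put the extra weeks in the denominator. That stands, and it answers the problem where event rates before and after stopping are alike. It does not answer it where they differ, since on- and off-treatment time are not separated, and it does not touch the crude percentages.

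**Collection need not stop at 4 weeks under Version 6.** Protocol 10.1 encourages subjects who stop dosing to stay in the study. Protocol 15.3.2 follows ongoing SAEs until they resolve or stabilize and keeps related SAEs reportable afterwards. This stands. A reader might take 8/12 = 67% as the share of post-treatment deaths lost under Version 6, but these provisions mean that the documents do not support that figure.

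**SAP 3.1 might look wrong** where it says "For subjects who are early terminated (ET), EOS visit is defined as the scheduled follow-up visit 4 weeks after last dose". It is a rule for assigning assessments to visits and does not end AE collection. Version 5 also had a follow-up visit 4 weeks after the last dose, so the text needs no correction.

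**A 28-day cut could hide relevant events.** Protocol 5.5 gives a half-life of about 1 month in the target CNS tissues, so later events may still bear on the drug. This is a good reason not to replace the main tables. It is no objection to a supplementary table.

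**The stakes are limited.** Safety is summarized by counts and percentages without tests, and the SAP already cautions about Part A/B. This affects the grade of the point but not its substance.

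**Conclusion.** The point holds as a gap in ascertainment and disclosure. The planned by-group percentages for the primary endpoint combine subjects with a scheduled 12-week post-dose window and subjects with a scheduled 4-week one, and the SAP neither equalizes nor mentions this.

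Two stronger readings are not supported. One is that a study group has a three-fold longer window. Three is a per-subject ratio, and it applies to a group comparison only if everyone in one group left before Version 6 and no one in the other did. The other is that Part A+B is biased upward. The SAP's remark on discontinuations gives no counts or dates and spans both studies, and early leavers are observed for less time overall, so the net direction could be the opposite.

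The size is 1.5 to 13.2 points of crude incidence for an affected subject who is event-free at the last dose. It rests on assumed constant rates of 0.1 to 1.0 per person-year and on completed 12-week follow-up. The effect on a group scales with shares that the documents do not give. The remedy is a cheap improvement and does not call for redesign of the analysis.

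**What to change.** - Keep the planned tables of all treatment-emergent events unchanged.
- In SAP 4.9.1, add supplementary by-group tables of AEs, SAEs and AEs leading to death with onset from the first dose to 28 days after the last dose, for every subject whatever the protocol version. For any rates in these tables, end person-time at the same point, or at the last day on study if earlier, so that numerator and denominator match. The Version 6 rationale itself treats 28 days as adequate monitoring.
- Tabulate events with onset more than 28 days after the last dose separately by group, with the number of subjects followed beyond day 28 as denominator.
- State how a partial onset date is placed relative to the cut.
- Add the change from 12 to 4 weeks of follow-up to SAP 2.3 and Table 2. Giving the number of subjects per group who ended under each schedule would let readers judge the imbalance.

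The cost is a few extra tables and one date comparison in the AE programs. No new data are needed and no safety event drops out of the report.
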